8.5. Follow-up of adverse events, serious adverse events, and pregnancies

8.5.1. Follow-up of adverse events and serious adverse events

8.5.1.1. Follow-up during the study

After the initial AE/SAE report, the investigator is required to proactively follow each subject and provide additional relevant information on the subject's condition to GSK Biologicals (within 24 hours for SAEs; refer to [Table 17](#)).

All SAEs documented at a previous visit/contact and designated as not recovered/not resolved or recovering/resolving will be reviewed at subsequent visits/contacts until the end of the study.

All AEs documented at a previous visit/contact and designated as not recovered/not resolved or recovering/resolving will be reviewed at subsequent visits/contacts until 30 days after the vaccination.

8.5.1.2. Follow-up after the subject is discharged from the study

The investigator will follow subjects:

- with SAEs or subjects withdrawn from the study as a result of an AE, until the event has resolved, subsided, stabilised, disappeared, or until the event is otherwise explained, or the subject is lost to follow-up.

If the investigator receives additional relevant information on a previously reported SAE, he/she will provide this information to GSK Biologicals using a paper/electronic Expedited Adverse Events Report and/or pregnancy report as applicable.

GSK Biologicals may request that the investigator performs or arranges the conduct of additional clinical examinations/tests and/or evaluations to elucidate as fully as possible the nature and/or causality of the AE or SAE. The investigator is obliged to assist. If a subject dies during participation in the study or during a recognised follow-up period, GSK Biologicals will be provided with any available post-mortem findings, including histopathology.

8.5.2. Follow-up of pregnancies

Pregnant subjects will be followed to determine the outcome of the pregnancy. At the end of the pregnancy, whether full-term or premature, information on the status of the mother and child will be forwarded to GSK Biologicals using the pregnancy report and the Expedited Adverse Events Report if applicable. Generally, the follow-up period doesn't need to be longer than six to eight weeks after the estimated date of delivery.

Regardless of the reporting period for SAEs for this study, if the pregnancy outcome is a SAE, it should always be reported as SAE.

8.6. Treatment of adverse events

Treatment of any AE is at the sole discretion of the investigator and according to current good medical practice. Any medication administered for the treatment of a SAE should be recorded in Expedited Adverse Event Report of the subject's eCRF (refer to Section 6.7).

8.7. Subject card

Study subjects/subjects' parent(s)/adoptive parent(s) must be provided with the address and telephone number of the main contact for information about the clinical study.

The investigator (or designate) must therefore provide a "subject card" to each subject/subject's parent(s)/adoptive parent(s). In an emergency situation this card serves

to inform the responsible attending physician that the subject is in a clinical study and that relevant information may be obtained by contacting the investigator.

Subjects/subjects' parent(s)/adoptive parent(s) must be instructed to keep subject cards in their possession at all times during the study duration.

9. SUBJECT COMPLETION AND WITHDRAWAL

9.1. Subject completion

A subject who returns for the concluding visit foreseen in the protocol is considered to have completed the study.

9.2. Subject withdrawal

Withdrawals will not be replaced.

9.2.1. Subject withdrawal from the study

From an analysis perspective, a 'withdrawal' from the study refers to any subject who did not come back for the concluding visit foreseen in the protocol.

All data collected until the date of withdrawal/last contact of the subject will be used for the analysis.

A subject is considered a 'withdrawal' from the study when no study procedure has occurred, no follow-up has been performed and no further information has been collected for this subject from the date of withdrawal/last contact.

Investigators will make an attempt to contact those subjects who do not return for scheduled visits or follow-up.

Information relative to the withdrawal will be documented in the eCRF. The investigator or delegate will document whether the decision to withdraw a subject from the study was made by the subject himself/herself, by the subject's parent(s)/adoptive parent(s), or by the investigator, as well as which of the following possible reasons was responsible for withdrawal:

- Serious adverse event.
- Unsolicited non-serious adverse event.
- Solicited adverse event
- Protocol violation (specify).
- Consent withdrawal, not due to an adverse event*.
- Moved from the study area.

- Lost to follow-up.
- Other (specify).

*In case a subject is withdrawn from the study because he/she/the subject's parent(s)/adoptive parent(s) has withdrawn consent, the investigator or delegate will document the reason for withdrawal of consent, if specified by the subject/subject's parent(s)/adoptive parent(s), in the eCRF.

Subjects who are withdrawn from the study because of SAEs/AEs must be clearly distinguished from subjects who are withdrawn for other reasons. Investigators will follow subjects who are withdrawn from the study as result of a SAE/AE until resolution of the event (see Section 8.5.1.2).

10. STATISTICAL METHODS

10.1. Primary endpoint

- Immunogenicity with respect to components of the study vaccine.
 - Anti-diphtheria* and anti-tetanus seroprotection status, one month after vaccination.
 - Anti-PT, anti-FHA and anti-PRN seropositivity status, one month after vaccination.

*Sera with ELISA concentrations <0.1 IU/ml will be tested for neutralising antibodies using a Vero-cell neutralisation assay.

10.2. Secondary endpoints

- Booster response* to the diphtheria, tetanus and pertussis (PT, FHA and PRN) antigens, one month after vaccination.
- Immunogenicity with respect to components of the study vaccine.
 - Anti-diphtheria** anti-tetanus, anti-PT, anti-FHA and anti-PRN antibody concentrations, one month after vaccination.
- Solicited local and general symptoms.
 - Occurrence of each solicited local and general symptom during the 4-day (Day 1-4) follow-up period after vaccination.
 - Occurrence of large swelling reactions during the 4-day (Day 1-4) follow-up period after vaccination.
- Unsolicited adverse events.
 - Occurrence of unsolicited AEs during the 31-day (Day 1-31) follow-up period after vaccination, according to the Medical Dictionary for Regulatory Activities (MedDRA) classification.

- Serious adverse events.
 - Occurrence of SAEs from the vaccination up to study end.

*Refer to Section 10.5 for the definition of booster response.

**Sera with ELISA concentrations <0.1 IU/ml will be tested for neutralising antibodies using a Vero-cell neutralisation assay.

10.3. Determination of sample size

The primary objective of the study is to assess the immunological response to the study vaccine in terms of seroprotection status for diphtheria, tetanus and in terms of seropositivity for the pertussis antigens, one month after vaccination.

According to Russian regulations, for the purpose of product registration, the minimum sample size required is 100 subjects in each age group. Therefore, the total number of evaluable subjects is 400 [100 subjects in each age group, 4-9 years (children), 10–17 years (adolescents), 18-64 years (adults) and ≥65 years (elderly population)]. Assuming a drop-out rate of 10%, to compensate for subject attrition due to early withdrawal, a total of 448 subjects (112 in each age group) will be enrolled in to the study in order to obtain the desired number of evaluable subjects for analysis.

Table 18, Table 19, Table 20 present the exact two-sided 95% confidence interval (CI) for a sample size of 400 subjects, according to the value observed for the seroprotection status for diphtheria and tetanus, seropositivity for the pertussis antigens and booster response to all antigens.

In addition, Table 21 presents the exact two-sided 95% CI for a sample size of 100 subjects (per age category), according to the value observed for the seroprotection status for diphtheria and tetanus, seropositivity for the pertussis antigens and booster response to all antigens.

Table 18 Exact two-sided 95% CI for a sample size of 400 subjects according to the value observed for seroprotection status for diphtheria and tetanus

Observed rate expressed as a percentage (number of subjects reporting seroprotection for diphtheria and tetanus antigens)	Exact two-sided 95% CI for this observed rate for a sample size of 400 subjects	
	Lower Limit	Upper Limit
90(360)	86.6	92.8
91.1(364)	87.8	93.6
95(380)	92.4	96.9
96.2(385)	93.9	97.9
99.5(398)	98.2	99.9
100(400)	99.1	100

Reference data: Please refer Table 22.

Table 19 Exact two-sided 95% CI for a sample size of 400 subjects according to the seropositivity for the pertussis antigens

Observed rate expressed as a percentage (number of subjects reporting seropositivity for the pertussis antigens)	Exact two-sided 95% CI for this observed rate for a sample size of 400 subjects	
	Lower Limit	Upper Limit
90(360)	86.6	92.8
95(380)	92.4	96.9
98.6(394)	96.8	99.4
99.1(396)	97.5	99.7
99.5(398)	98.2	99.9
100(400)	99.1	100

Reference data: Please refer [Table 22](#).

Table 20 Exact two-sided 95% CI for a sample size of 400 subjects according to the value observed for the primary endpoints and the Booster response to all antigens

Observed rate expressed as a percentage (number of subjects reporting Booster response to all antigens)	Exact two-sided 95% CI for this observed rate for a sample size of 400 subjects	
	Lower Limit	Upper Limit
75(300)	70.5	79.2
79(316)	74.7	82.9
80(320)	75.7	83.8
80.6(322)	76.3	84.3
81.2(325)	77.1	85
84.6(338)	80.6	87.9
85(340)	81.1	88.4
89.3(357)	85.8	92.1
90(360)	86.6	92.8
92.1(368)	88.9	94.5
92.8(371)	89.8	95.1
94.3(377)	91.5	96.3
95(380)	92.4	96.9
96.8(387)	94.5	98.3
98.9(396)	97.5	99.7
99.5(398)	98.2	99.9
100(400)	99.1	100

Reference data: Please refer [Table 22](#).

Table 21 Exact two-sided 95% CI for a sample size of 100 (per age category) subjects according to the value observed for the seroprotection status for diphtheria and tetanus, seropositivity for the pertussis antigens and booster response to all antigens.

Observed rate expressed as a percentage (number of subjects reporting Booster response to all antigens)	Exact two-sided 95% CI for this observed rate for a sample size of 100 subjects	
	Lower Limit	Upper Limit
75(75)	65.3	83.1
79(79)	69.7	86.5
80(80)	70.8	83.8
81(81)	71.9	88.2
84(84)	75.3	90.6
85(85)	76.5	91.4
89(89)	81.2	94.4
90(90)	82.4	95.1
92(92)	84.8	96.5
94(94)	87.4	97.8
95(95)	88.7	98.4
96(96)	90.1	98.9
98(98)	93.0	99.8
99(99)	94.6	100.0
100(100)	96.4	100.0

Reference data: Please refer [Table 22](#).

Table 22 Reference values

Study	Country	Population (Age in Years)	Vaccination History	N	D	T	PT	FHA	PRN	D VR	T VR	PT VR	FHA VR	PRN VR
DTPA (BOOSTRIX-045) 114778	Mexico, Chile	10-15	5/6X DTPa	319	100	100	99.1	100	100	79	84.6	92.8	96.5	99.7
DTPA (BOOSTRIX-002) 263855/002	Australia	<40	Heterogeneous	214	96.2	100	99.5	100	100	-	-	96.2	100	99.1
DTPA (BOOSTRIX-002) 263855/002	Australia	≥40	Heterogeneous	214	91.1	99.5	98.6	100	99.1	-	-	94.3	99.5	98.1
DTPA (BOOSTRIX-004) 263855/004	Finland	10-14	4XDTPw	447	100	100	98.4	100	100	-	-	92.1	96.8	98.9
DTPA (BOOSTRIX-029) 263855/029	Belgium	10-18	4XDTPw	218	99.5	100	100	100	100	80.6	81.2	89.3	97.7	98.1
(APV-118) 208355/118	Germany	4-6	4XDTPa	172	100	100	100	100	100	-	-	98.3	91.1	94.8
DTPA (BOOSTRIX-034) 263855/034	Belgium	≥40	Heterogeneous	139	99.3	100	100	100	100	89.6	85.9	98.5	99.3	97.7
DTPA (BOOSTRIX)-041 BST 029 (113055)	Belgium	20-28	4XDTPw + booster DTPa	60	100	100	100	100	100	-	-	94.1	96.0	67.3

N = number of subjects included in the PP cohort for immunogenicity

D and T: % of subjects with antibody concentration ≥0.1 IU/ml; PT, FHA and PRN: % of subjects with antibody concentration ≥5 EL.U/ml.

VR= Vaccine response:

Booster responses to the diphtheria and tetanus antigens, defined as:

For subjects with pre-vaccination concentration below seroprotection cut-off (<0.1 IU/ml): antibody concentrations at least ≥0.4 IU/ml one month after vaccination.

For subjects with pre-vaccination concentration equal or above seroprotection cut-off (≥0.1 IU/ml): an increase in antibody concentrations of at least four times the pre-vaccination concentration one month after vaccination.

Booster response to the PT, FHA and PRN antigens, defined as:

For initially seronegative subjects (pre-vaccination concentration below cut-off: <5 EL.U/ml): antibody concentrations at least four times the cut-off (post-vaccination concentration ≥20 EL.U/ml)

For initially seropositive subjects with pre-vaccination concentration ≥5 EL.U/ml and <20 EL.U/ml: an increase in antibody concentrations of at least four times the pre-vaccination concentration.

For initially seropositive subjects with pre-vaccination concentration ≥20 EL.U/ml: an increase in antibody concentrations of at least two times the pre-vaccination concentration.

10.4. Cohorts for Analyses

Two cohorts are defined for the purpose of analysis:

- The Total vaccinated cohort (TVC).
- PP cohort for analysis of immunogenicity.

10.4.1. Total vaccinated cohort

- The TVC analysis will be performed per treatment actually administered. A safety analysis based on the TVC will include all subjects with the study vaccine administration documented.
- An immunogenicity analysis based on the TVC will include all subjects vaccinated and for whom data concerning at least one immunogenicity endpoint measure is available.

10.4.2. Per protocol cohort for analysis of immunogenicity

The PP cohort for immunogenicity will include all evaluable subjects:

- Who have received the dose of study vaccine.
- For whom administration site of study vaccine is known and according to the protocol.
- Who have not received a vaccine not specified or forbidden in the protocol.
- Who meet all eligibility criteria.
- Who comply with the procedures and intervals defined in the protocol (Refer to [Table 6](#)).
- Who are within the maximum interval (the interval between Visit 1 and blood sampling at Visit 2, considered for inclusion of a subject will be 21–48 days) allowed as defined in the protocol.
- Who do not meet any of the criteria for elimination from an PP analysis (refer to [Section 6.7.2](#)).
- Who did not receive a product leading to exclusion from an PP analysis (refer to [Section 6.7.2](#)).
- Who did not present with a medical condition leading to exclusion from an PP analysis (refer to [Section 6.8](#)).
- For whom data concerning immunogenicity endpoint measures are available. This will include subjects for whom assay results are available for antibodies against at least one study vaccine antigen component.

10.5. Derived and transformed data

- A seronegative subject is a subject whose antibody concentration is below the assay cut-off value.
- A seropositive subject is a subject whose antibody concentration is greater than or equal to the assay cut-off value.
- A seroprotected subject is a subject whose antibody concentration is greater than or equal to the level defining clinical protection. The following seroprotection thresholds are applicable:
 - Anti-diphtheria antibody concentrations ≥ 0.1 IU/ml *for ELISA assay and ≥ 0.1 IU/ml for Vero-cell assay. (Amended 31 October 2017)*
 - Anti-tetanus antibody concentrations ≥ 0.1 IU/ml.
- Other cut-offs to be considered:
 - Anti-diphtheria antibody concentrations ≥ 1.0 IU/ml.
 - Anti-tetanus antibody concentrations ≥ 1.0 IU/ml.
- Booster response to Diphtheria and Tetanus antigens is defined as:
 - for subjects with pre-vaccination antibody concentration < 0.1 IU/ml (i.e. below the seroprotection cut-off), antibody concentrations at least ≥ 0.4 IU/ml, one month after vaccination, and
 - for subjects with pre-vaccination antibody concentration ≥ 0.1 IU/ml (i.e. equal or above the seroprotection cut-off), an increase in antibody concentrations of at least four times the pre-vaccination concentration, one month after vaccination.
- Booster response to PT, FHA and PRN antigens is defined as:
 - for subjects with pre-vaccination antibody concentration below the assay cut-off, post-vaccination antibody concentration \geq four times the assay cut-off,
 - for subjects with pre-vaccination antibody concentration between the assay cut-off and below four times the assay cut-off, post-vaccination antibody concentration \geq four times the pre-vaccination antibody concentration, and
 - for subjects with pre-vaccination antibody concentration \geq four times the assay cut-off, post-vaccination antibody concentration \geq two times the pre-vaccination antibody concentration.
- The geometric mean concentration (GMC) calculations are performed by taking the anti-log of the mean of the \log_{10} concentration transformations. Antibody concentrations below the cut-off of the assay will be given an arbitrary value of half the cut-off for the purpose of GMC calculation.

Handling of missing data:**Immunogenicity:**

- For a given subject and a given immunogenicity measurement, missing or non-evaluable measurements will not be replaced.

Reactogenicity and Safety:

- For a given subject and the analysis of solicited symptoms during the 4-day post-vaccination follow-up period, missing or non-evaluable measurements will not be replaced. Therefore, the analysis of the solicited symptoms based on the TVC will include only vaccinated subjects and doses with documented safety data (i.e. symptom screen completed).
- For analysis of unsolicited AEs, such as SAEs or AEs by primary MedDRA term, and for the analysis of concomitant medications, all vaccinated subjects will be considered. Subjects who did not report the event or the concomitant medication will be considered as subjects without the event or the concomitant medication, respectively.
- For summaries reporting both solicited and unsolicited AEs, all vaccinated subjects will be considered. Subjects who did not report the event or the concomitant medication will be considered as subjects without the event or the concomitant medication, respectively.

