5.7.5. Immunological correlates of protection

The following cut-offs are accepted as immunological correlates of protection:

- Specific antibodies against diphtheria toxoid (anti-diphtheria) and tetanus toxoid (anti-tetanus) will be measured by enzyme-linked immunosorbent assay (ELISA). The newly validated assay cut-off for anti-diphtheria is currently set at 0.057 IU/ml and for anti-tetanus at 0.043 IU/ml. For both serology a threshold of 0.1 IU/ml provides a conservative estimate of the percentage of subjects deemed to be protected [Camargo, 1984; Melville-Smith, 1983].
- The cut-off of the Vero-cell neutralisation assay (performed for pre- and post-vaccination serum samples when ELISA anti-diphtheria antibody concentrations are <0.1 IU/ml) is 0.004 IU/ml. Antibody concentrations ≥ 0.01 IU/ml are considered as protective [WHO, 1994]. **Both the ELISA test (antibody concentrations ≥ 0.1 IU/ml) and Vero-cell test (antibody concentration ≥ 0.01 IU/ml) will define the seroprotection status for the primary endpoint. (Amended 31 October 2017)**
- No serological correlate of protection is defined for the immune response to pertussis antigens. Antibodies against the pertussis components PT, FHA and PRN will be measured by ELISA technique. The newly validated assay cut-off for anti-PT is 2.693 IU/ml, for anti-FHA is 2.046 IU/ml and for anti-PRN is 2.187 IU/ml. Subjects with antibody concentration below this cut-off will be considered seronegative.

The immunological assay results will be communicated to the investigator as soon as they become available.

The investigator is encouraged to share the immunological assay results for non-responders with the study subjects/subjects' parent(s)/adoptive parent(s).

For the subjects identified as non-responders, it remains the responsibility of the investigator in charge of the subject's clinical management to determine the medical need for re-vaccination and to re-vaccinate the subjects as per local/regional practices.

Non-responders are defined as:

- Antibody concentrations <0.01 IU/ml post-booster for diphtheria antigen by Vero-cell neutralisation assay and,
- Antibody concentrations <0.1 IU/ml post-booster for tetanus antigen by ELISA assay.

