10.7. Analysis of immunogenicity

The primary analysis will be based on the PP cohort for analysis of immunogenicity. If, the percentage of vaccinated subjects with serological results excluded from the PP cohort for analysis of immunogenicity is 5% or more, a second analysis based on the TVC will be performed to complement the PP analysis.

For all subjects and each antigen:

- Seropositivity/seroprotection rate at pre-vaccination and one month post-vaccination will be calculated with exact 95% CIs.
- GMCs at pre-vaccination and one month post-vaccination will be tabulated with 95% CIs.
- Booster response rate one month post-vaccination will be calculated with exact 95% CIs for diphtheria, tetanus and pertussis antigens.

In addition, the above analysis will also be done based on age stratification (Refer [Table 23](#)) as an exploratory analysis.

Finally, antibody concentrations distribution at pre-vaccination and one month post-vaccination will be displayed using reverse cumulative curves (RCC).

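### Section 10.5 sets the Vero-cell threshold for diphtheria seroprotection at 0.1 IU/ml; Section 5.7.5 sets it at 0.01 IU/ml for the same primary endpoint

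*Protocol*

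**What the plan says.** Anti-diphtheria seroprotection status one month after vaccination is part of the primary endpoint (Protocol Section 10.1). The footnote there sends sera below 0.1 IU/ml by ELISA to a second assay: "IU/ml will be tested for neutralising antibodies using a Vero-cell neutralisation assay". It gives no threshold for that assay.

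Two sections supply one:

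- **Section 10.5 (Derived and transformed data)** lists the seroprotection thresholds. For diphtheria it gives 0.1 IU/ml or more by ELISA and at least "0.1 IU/ml for Vero-cell assay".
- **Section 5.7.5 (Immunological correlates of protection)** pairs ELISA at 0.1 IU/ml or more with a Vero-cell limit of "0.01 IU/ml) will define the seroprotection status for the primary endpoint". It also says of the Vero-cell assay that concentrations of at least "0.01 IU/ml are considered as protective". Its diphtheria non-responder limit is a result below "0.01 IU/ml post-booster for diphtheria antigen by Vero-cell neutralisation assay and".

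Both lines are marked as amended on 31 October 2017. Section 10.7 then plans the summary: "Seropositivity/seroprotection rate at pre-vaccination and one month post-vaccination will be calculated with exact 95% CIs".

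**The concern.** The Vero-cell test is run only on sera that fall below the ELISA limit, so it alone decides the status of those subjects. The conflict lies exactly there. With two thresholds a factor of ten apart, one part of the primary endpoint has two definitions.

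Section 10.5 is where a programmer would look for the derivation rule. Its value would raise no suspicion, because it matches the ELISA and tetanus thresholds beside it. Following it would give a diphtheria rate equal to or lower than the one Section 5.7.5 defines. Under Section 10.5 there would also be subjects who are neither seroprotected nor non-responders by the Vero-cell criterion.

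The data are meant to support registration (Section 1.2.1), and there is no comparator and no hypothesis test. The reported rate and interval are the result. If the choice between sections were made after the data were seen, it could not be shown to have been pre-specified.

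**Working it through.** **1. The two rules side by side, for a post-booster serum**

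| ELISA (IU/ml) | Vero-cell (IU/ml) | Section 5.7.5 | Section 10.5 |
|---|---|---|---|
| ≥0.1 | not tested | seroprotected | seroprotected |
| <0.1 | ≥0.1 | seroprotected | seroprotected |
| <0.1 | 0.01 to <0.1 | **seroprotected** | **not seroprotected** |
| <0.1 | <0.01 | not seroprotected | not seroprotected |

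Only the third row differs. Section 10.1 does not settle it, because it names no Vero-cell threshold.

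**2. The plan's own figures reproduce**

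- Enrolment: 100 / (1 − 0.10) = 111.1, rounded up to 112 per stratum; 4 × 112 = 448. This does not depend on the threshold.
- Exact (Clopper-Pearson) 95% intervals: 364/400 gives 87.8 to 93.6, as in Table 18; 90/100 gives 82.4 to 95.1, as in Table 21.

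**3. Inputs for the size**

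The protocol gives no Vero-cell distribution. The Table 22 note ("D and T: % of subjects with antibody concentration" at or above 0.1 IU/ml) does not name the assay. The following are therefore assumptions:

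- The Table 22 diphtheria rates stand for ELISA rates.
- 100 subjects are evaluable in each of the four strata (Section 10.3).
- The two younger strata are at 100%; the child and adolescent rows of Table 22 run from 99.5 to 100%.
- A fraction *f* of the ELISA-low sera has a Vero-cell result from 0.01 to below 0.1 IU/ml. *f* is unknown and is varied from 0 to 1.

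With 100 subjects per stratum, the percentage below 0.1 IU/ml is also the expected number of subjects: 100 − 91.1 = 8.9; 100 − 96.2 = 3.8; 100 − 99.3 = 0.7.

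**4. Pooled shift in the diphtheria rate**

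Shift = *f* × (ELISA-low subjects in the two adult strata) / 400.

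| Assumed adult rates (18-64 / ≥65) | ELISA-low subjects | *f* = 0.25 | *f* = 0.5 | *f* = 1 |
|---|---|---|---|---|
| 91.1% / 91.1% | 17.8 | 1.1 points | 2.2 points | 4.5 points |
| 96.2% / 91.1% | 12.7 | 0.8 points | 1.6 points | 3.2 points |
| 99.3% / 99.3% | 1.4 | 0.09 points | 0.18 points | 0.35 points |

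At *f* = 0 the shift is zero in every row. At the extreme of the first row (17.8 rounded to 18 subjects):

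- Section 10.5: 382/400 = 95.5%, exact 95% CI 93.0 to 97.3.
- Section 5.7.5: 400/400 = 100%, exact 95% CI 99.1 to 100.

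**5. One adult stratum (n = 100, exploratory)**

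At 91.1% the shift is up to 8.9 points. Rounded to 9 subjects, that is 91/100 (83.6 to 95.8) against 100/100 (96.4 to 100). At the 99.3 to 100% of six of the eight Table 22 rows it is at most 0.7 points.

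**The case against.** The strongest reply is that this is a dropped zero. The Amendment 3 log in Appendix B gives 0.01 IU/ml as the wording for Section 10.5, the value it also gives for Section 5.7.5. Section 5.7.5 is the more specific text and uses 0.01 three times. The intention is therefore hardly in doubt, and a text-extraction fault in Section 10.5 cannot be excluded entirely.

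Most of this stands as an account of the cause. The log is good evidence of intent, but it does not correct the current text, and the conflict between the two sections exists without it. Nothing confirms an extraction fault.

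A second reply is that little depends on it. The trial is descriptive with no success criterion, and sample size, interval tables, tetanus and pertussis are unaffected. The upper bound also takes the lowest Table 22 rate, from a population aged 40 and over, for both adult strata and puts every ELISA-low serum in the disputed band. That is fair: 4.5 points is an extreme, and the true effect may be near zero. It limits the size but does not give the endpoint a single definition.

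A third point concerns the repair. Section 5.7.5 says that both tests define status and does not spell out a sequence. That is correct, but Section 10.1 supplies one: the Vero-cell assay is run only when ELISA is below 0.1 IU/ml. Requiring both limits to be met would then leave the second test without any effect.

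**Conclusion.** The concern holds. Two current sections define diphtheria seroprotection with Vero-cell thresholds that differ tenfold, and no other current section resolves it. If Section 10.5 were followed, the primary diphtheria rate could be understated relative to the Section 5.7.5 definition and could never be overstated.

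Under the assumptions above, the pooled understatement is at most 0.35 points with 99.3% in both adult strata and 0 to 4.5 points with 91.1% in both. Within one adult stratum it could reach 8.9 points. The protocol does not give the share of sera in the disputed band, so no point estimate is possible. The contradiction itself rests on no assumption. It should be corrected before analysis because it concerns the definition of a primary endpoint, even though the numerical effect may be small.

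**What to change.** Before the analysis, amend the diphtheria line in Section 10.5 to agree with Section 5.7.5 and state the testing sequence from Section 10.1. Suggested wording:

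> Seroprotected against diphtheria: ELISA ≥0.1 IU/ml or, if ELISA <0.1 IU/ml, Vero-cell ≥0.01 IU/ml (as in Section 5.7.5).

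The analysis programs and any separate analysis plan should carry the same rule, for both the pre-vaccination and the one-month rates in Section 10.7.

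The cost is one line of protocol wording. Data, visits, samples, assays and the enrolment of 448 do not change.
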